8.6.9 Physical Examinations

Physical examination data will be presented in a data listing.

8.6.10 Electrocardiogram

ECG parameters will be summarized by treatment group using descriptive statistics. In order to assess the QT interval data, corrected QT (QTc) values will be calculated based on the following three methods.

- 1) Fridericia's correction: QTc=QT/RR0.33,
- 2) Bazett's Correction: QTc=QT/RR0.5,

And

3) Correction based on linear regression techniques: Based on the data from baseline study population, the intercept(a) and slope (b) will be estimated separately for males and females using the equation QT=a+b(1-RR). Those estimates will be used to calculate the corrected QT values at post baseline time points.

Confidential

QTc interval data at post-baseline visits will then be summarized descriptively by central tendency techniques. In addition, the frequency counts and percentages by treatment group for the following categories will be provided:

>450 with Baseline <=450,
>480 with Baseline <=480,
>500 with Baseline <=500,
Increases from baseline > 30 and
Increases from baseline > 60

8.7 Statistical and Analytical Issues

8.7.1 Adjustment for Covariates

Efficacy analyses will be adjusted for country and baseline values.

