8.2 Determination of Sample Size

The information below provides the background information for sample size determination for the induction of clinical remission with endoscopic response at 16 weeks followed by clinical and endoscopic remission at 52 weeks. For placebo, the expected rates are based on data from a Phase 2 study (RETIC 03/06) conducted in subjects with active moderate Crohn's disease. The rates for Rifaximin DR are based on the assumption that Rifaximin DR will provide a somewhat higher induction of remission rate.

Expected rates for induction of clinical remission with endoscopic response at Week 16 are 40% for placebo and 55% for Rifaximin DR.

Based on a significance level of 5% (alpha 0.05), a sample size of approximately 240 subjects per treatment group will have at least 90% power to test the hypothesis that Rifaximin DR is superior to placebo for each co-primary endpoint considered individually. Approximately 80% power is available to detect significant differences between Rifaximin DR and placebo for both co-primary endpoints.

For the Long Term Treatment Phase, a 15% treatment effect is expected for both clinical symptom and endoscopic remission at Week 52. Based on this assumption and testing at a significance level of 5% (alpha 0.05), a sample size of approximately 210 subjects per treatment group will have at least 90% power to test the key secondary efficacy hypothesis that Rifaximin DR is superior to placebo when each key co-secondary endpoint is considered individually. In addition, approximately 80% power is available to detect significant differences between Rifaximin DR and placebo for each of the key co-secondary endpoints.

An additional consideration for sample size determination is the application of an inflation factor of 20% to account for drop-out rates during the Induction and Long Term Treatment Phases of the study. This consideration suggested that 330 subjects per treatment group would be required at study entry.

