8.6 Analysis Methods

The phrases 'statistical analysis' or 'analysis' will be used to mean inferential analysis (such as performing tests of significance, reporting p-values and confidence intervals). When no inferential analysis will be performed, the phrases 'descriptive analysis' or 'descriptive statistics' will be used (for instance, producing summary tables of means, standard deviations, percentages of responders). All efficacy analyses will be conducted on ITT and PP populations. All efficacy analyses will adjust for country.

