8.6.1 Primary Efficacy Analysis

Induction Phase

There will be two co-primary measures of efficacy assessed during the Induction Phase. The first co-primary endpoint is:

 Clinical symptom remission defined by (1) the total number of liquid/very soft stools for the 7 days prior to the Week 16 visit being ≤ 10 (from CDAI Item 1); AND (2) an abdominal pain rating of ≤ 1(from CDAI Item 2) on each day for the 7 days prior to the Week 16 visit.

The second co-primary endpoint is:

 Endoscopic response defined as a ≥3-point decrease in the SES-CD from baseline to the SES-CD score obtained between Week 16 and Week 17. SES-CD scores will be calculated from centrally-read digital video of ileocolonoscopies performed at baseline and between Week 16 and Week 17.

For each endpoint, the null hypothesis H0: πR - πP =0 versus the alternative HA: πR - $\pi P \neq 0$ is of interest, where πR is the binomial parameter for induction of remission/response for the

Rifaximin DR group, and πP is the binomial parameter for induction of remission/response for the placebo group. Subjects who require the initiation of rescue medication and/or surgery for CD will be considered treatment failures from the date of the introduction of the rescue medication and/or surgery, regardless of their actual response data. The Cochran-Mantel-Haenszel (CMH) test, stratified by country, will be used to test the hypothesis. Each null hypothesis of no difference will be rejected if the resulting p-value for the respective statistical test is less than 0.05. Significance for the induction claim will only be declared if both null hypotheses are rejected. As such, the overall Type I error rate will be maintained at the 5% level without adjustment for multiple comparisons.

If it is evident that the response variable is confounded with some of the background variables, then logistic regression will be performed using the background variables as covariates. The differences between this adjusted analysis and the previous unadjusted analysis will be noted, and the impact of such differences will be discussed.

The primary efficacy analysis will be repeated on the PP population to assess the robustness of the results of the primary outcome.

Long Term Treatment Phase

There will be two key co-secondary endpoints of efficacy assessed during the Long Term Treatment Phase. The first is:

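### Section 8.7.1 promises adjustment for baseline values, but the co-primary and key co-secondary tests adjust for country only and add a covariate model only if the data seem to call for it; the cost is a modest missed gain in precision

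*Protocol*

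**What the plan says.** Three places in the protocol set the covariate rule.

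- Section 8.7.1 (Adjustment for Covariates): "Efficacy analyses will be adjusted for country and baseline values". Binary endpoints are not excepted.
- Section 8.6 (Analysis Methods): "All efficacy analyses will adjust for country". Baseline is not mentioned.
- Section 8.6.1, for each Week 16 co-primary endpoint: "The Cochran-Mantel-Haenszel (CMH) test, stratified by country, will be used to test the hypothesis". The decision rule follows: "Each null hypothesis of no difference will be rejected if the resulting p-value for the respective statistical test is less than 0.05". The Long Term Treatment Phase text repeats the same test and rule for the two Week 52 endpoints.

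For both phases, 8.6.1 then adds: "If it is evident that the response variable is confounded with some of the background variables, then logistic regression will be performed". The covariates are described only as background variables. Differences from the CMH, which this paragraph calls the unadjusted analysis, are to be noted and their impact discussed.

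Section 8.6.2 carries the CMH approach over to the other binary endpoints. Only its models for continuous outcomes include the baseline value.

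**The concern.** A statistician following 8.7.1 and one following 8.6.1 would not run the same analysis of the four most important endpoints. The protocol should leave no doubt about which is meant.

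The conditional paragraph is a second weakness. Whether response is confounded with a background variable can be judged only by looking at response. The protocol gives no criterion for evident. In a randomised trial, chance imbalance does not invalidate the test, so it is a poor reason to adjust. Covariates earn their place by being prognostic, and that choice is made in advance.

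The third issue is unused information. Inclusion criteria 3 and 4 require an SES-CD score, an average daily pain score and an average daily liquid stool count from every subject before randomisation. Both co-primary endpoints must be significant for the induction claim, so a small gain on each carries through to the joint result.

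**Working it through.** **Inputs from the protocol.** Section 8.2: "Expected rates for induction of clinical remission with endoscopic response at Week 16 are 40% for placebo and 55% for Rifaximin DR"; "a sample size of approximately 240 subjects per treatment group will have at least 90% power"; about 80% power for both endpoints; 20% drop-out allowance; 330 per group at entry. Section 8.6.1: each test at 0.05 against a two-sided alternative, both to be rejected. Section 8.7.2: subjects with missing data count as non-responders.

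**Formula.** Power = Φ{(d − 1.96·s0)/s1}, where d is the difference in rates, s0 the standard error with the pooled rate, and s1 the standard error with separate rates.

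**1. The plan's own figure.** With 240 per group and 40% v 55%: s0 = √(2 × 0.475 × 0.525/240) = 0.0456; s1 = √((0.40 × 0.60 + 0.55 × 0.45)/240) = 0.0451. Power = Φ{(0.15 − 0.0893)/0.0451} = Φ(1.346) = 91.1%. Jointly, if the endpoints are independent, 0.911² = 83.0%. For 90% power, n is 231 per group without and 244 with continuity correction. The stated 240 is consistent with this, and the calculation uses no covariate adjustment.

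**2. Country-only test with drop-outs as failures.** Assume the full 20% are missing and score as failures: 0.8 × 40% = 32%; 0.8 × 55% = 44%. With 330 per arm, s0 = 0.0378 and s1 = 0.0375. Power = Φ{(0.12 − 0.0741)/0.0375} = Φ(1.225) = 89.0%. Jointly, under independence, 79.2%.

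**3. Adding baseline.** The protocol does not say how strongly baseline predicts outcome, so the share of variance explained (R²) is an assumed range. Both variances are multiplied by 1 − R².

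| R² (assumed) | Power per endpoint | Both (independent) |
|---|---|---|
| 0 | 89.0% | 79.2% |
| 5% | 90.5% | 81.8% |
| 10% | 91.9% | 84.5% |
| 15% | 93.3% | 87.0% |

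The gain per endpoint is about 1.5 to 4 points.

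**4. Which R² this is.** The table applies R² to the outcome as analysed, with drop-outs already scored as failures. If missingness is unrelated to baseline, that scoring dilutes R² by the factor 0.8² × (0.475 × 0.525)/(0.38 × 0.62) = 0.68. An R² of 5, 10 or 15% for the complete outcome then becomes 3.4, 6.8 or 10.2%, and power 90.0, 91.0 or 91.9%: a gain of about 1 to 3 points.

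**5. Cross-check by simulation.** 240 per group, 40% v 55%, one baseline covariate, no country strata, 6,000 runs per setting. For odds ratios per standard deviation of 1.35, 1.65, 2.2 and 2.7, the unadjusted test had power 91.1, 91.4, 90.8 and 91.6%; logistic regression with the covariate had 92.0, 92.2, 93.9 and 95.3%. With a covariate of no prognostic value the two were 90.3% and 90.4%.

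**The case against.** The strongest reply is that 8.7.1 names no test or model, whereas 8.6.1 names the test and ties rejection to it. On that reading 8.7.1 is a loose summary of the continuous-endpoint models in 8.6.2, which do carry country and baseline. This stands to the extent that the CMH is the decision test. It does not remove the contradiction, because 8.7.1 speaks of efficacy analyses in general.

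A reader might go further and infer that the plan has two rival primary results and an inflated error rate. In the simulation, claiming success on whichever of the two analyses was significant gave a type I error of 5.9, 5.6, 7.1 and 7.1% over the four covariate strengths (Monte Carlo standard error about 0.3 points). The protocol does not permit that substitution. The regression is additional, and its differences from the CMH are only noted and discussed.

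A second reply is that unnamed covariates are a matter for the statistical analysis plan, which section 8.0 says will be final before database lock. That is fair for the list of covariates. It does not cover the data-dependent trigger, which the protocol itself lays down.

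A third is that the precision gain is assumed. This also stands. The entry criteria narrow the baseline range (CDAI 220 to 450, SES-CD at least 7, mean pain and daily stools above 1.5), which may weaken prediction. On the other side, response is at most 10 liquid stools a week and entry requires more than 1.5 × 7 = 10.5, so subjects start at very different distances from the threshold. That makes prognostic value plausible but does not size it.

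Finally, a country-stratified CMH is a valid, standard test. Agreed: moving to a baseline-adjusted model is an improvement, not the repair of an invalid analysis.

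**Conclusion.** The point holds as an inconsistency fixed in the protocol text, together with an unsound trigger for a supportive analysis. Type I error is 5% as long as the CMH alone supports each claim; the triggered model affects supportive interpretation only.

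One might also infer that the trial is underpowered. It is not: the plan's 90% figure reproduces, and even with 20% scored as failures the country-only test has about 89% power per endpoint and 79% for both under independence, against a planned figure of about 80%. What is forgone is about 1.5 to 4 points per endpoint if baseline explains 5 to 15% of the variance of the outcome as analysed, less if drop-out scoring dilutes that share, and close to nothing if baseline is not prognostic. These sizes rest on the assumed R², on 20% missing at Week 16 in both arms and, for the joint figures, on independent endpoints. They were worked for Week 16 only.

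**What to change.** Bring 8.6, 8.6.1 and 8.7.1 into line and name one deciding analysis for the four endpoints before unblinding. The preferred form is a prespecified logistic model with treatment, country and the matching baseline value: SES-CD for the endoscopic endpoints, weekly liquid stool count and mean pain for the symptom endpoints. Report it as a standardised risk difference, which keeps the result on the scale of the hypotheses in 8.6.1. Keep the country-stratified CMH as supportive. Stratifying the CMH further by baseline category is not advised, since about 660 subjects spread over many countries would leave sparse strata. Delete the conditional logistic-regression paragraphs for both phases.

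At minimum, if the CMH stays decisive, say so, limit 8.7.1 to the continuous endpoints, and make the baseline-adjusted logistic model an unconditional, prespecified supportive analysis.

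The cost is wording in three sections and a little programming. No new data are needed.

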8.7.2 Handling of Dropouts or Missing Data

Missing data will be handled using the Worst Case analysis method for the primary and key secondary endpoints. In the Worst Case analysis, subjects with fewer than 4 days of diary data in a given week will be considered non-responders for that week. Additionally, subjects with missing SES-CD data will be classified non-responder for that measure in that week.

The following three sensitivity analyses will be conducted to address the impact of missing data on the primary and key secondary endpoints:

Last Observation Carried Forward (LOCF) Analysis: In the first analysis, missing values will be replaced with the last previous non-missing value. The baseline values will not be carried forward.

Multiple Imputation Analysis: In the second analysis, missing values will be filled in by the multiple imputation method which involves the following distinct phases:

- The missing data will be filled in to generate complete data sets using SAS/STAT procedure PROC MI;
- The complete data sets will be analyzed using PROC LOGISTIC in SAS/STAT;
- The above two steps will be repeated 5 times;
- The results from the complete data sets will be combined for statistical inferenceusing SAS/STAT procedure PROC MIANALYZE.

Observed Case Analysis: In the third analysis, subjects are excluded from the analysis if the subject has insufficient data to be determined as a responder or non-responder in a given 4-week assessment period. This analysis is not based on the ITT population and, therefore, interpretation of results from this analysis requires substantial caution. This is because the subjects who responded in the respective treatment groups may have different distributions for background characteristics. Thus, additional analysis may be undertaken by the use of statistical methods which provide adjustment for background characteristics.

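### Five imputations leave the multiple imputation sensitivity analysis noisy enough for a borderline p-value to cross 0.05 on a rerun; raise the number to about 50-100 and fix the seed

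*Protocol*

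**What the plan says.** Section 8.7.2 sets the main missing-data rule: "Missing data will be handled using the Worst Case analysis method for the primary and key secondary endpoints". Subjects with too little diary data or no endoscopy score count as non-responders, so this rule involves no random draw.

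The section then adds LOCF, multiple imputation and observed-case analyses: "The following three sensitivity analyses will be conducted to address the impact of missing data on the primary and key secondary endpoints". For multiple imputation, PROC MI fills in the data and then "The complete data sets will be analyzed using PROC LOGISTIC in SAS/STAT". The number of imputations is fixed: "The above two steps will be repeated 5 times". PROC MIANALYZE combines the results. No seed and no model terms are given.

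The primary test in section 8.6.1 is different: "The Cochran-Mantel-Haenszel (CMH) test, stratified by country, will be used to test the hypothesis". Its decision rule is "Each null hypothesis of no difference will be rejected if the resulting p-value for the respective statistical test is less than 0.05", and both co-primary hypotheses must be rejected. Section 8.6 adds a general rule: "All efficacy analyses will adjust for country". Section 8.7.1 names baseline values as well as country.

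**The concern.** Five imputations are usually defended by relative efficiency, which is high even for small numbers. Efficiency describes the variance of the pooled estimate. It does not say how far the p-value moves when the same data are imputed again with another seed.

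The number is written into the protocol, so an SAP that follows the protocol inherits it.

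This analysis also carries some weight among the three checks. Section 8.7.2 itself urges caution with the observed-case analysis. LOCF does not carry baseline values forward, and the first scheduled post-baseline ileocolonoscopy is the one after Week 16. For the Week 16 endoscopic co-primary, LOCF therefore has nothing to carry unless an endoscopy was obtained at early withdrawal, as section 4.5 asks. If the multiple imputation result is borderline, a reader could not tell agreement or disagreement with the primary analysis from chance in the draws.

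**Working it through.** **Inputs.** From the protocol: m = 5 (8.7.2); two-sided 0.05 (8.6.1); 40% vs 55% with about 240 per arm and at least 90% power, one 20% drop-out factor, and 330 per arm randomized (8.2). Assumed: FMI, which the protocol does not give, from 0.10 to 0.36.

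**The plan's own figures.** The choice of 5 has no derivation, so there is nothing to reproduce for it. The power claim does reproduce: 240 per arm at 40% vs 55% gives 91.1%. The expected z at those rates is 0.15 / sqrt(2 x 0.475 x 0.525 / 240) = 3.29.

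**Seed-to-seed noise.** In units of the standard error, the pooled z varies between seeds with SD = sqrt(FMI/m). Relative efficiency is 1/(1 + FMI/m). A p-value of 0.025 with unlimited imputations corresponds to z = 2.241. The 95% range over seeds is the p-value at 2.241 ± 1.96 x SD.

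| FMI | m | SD of z | Relative efficiency | 95% range of p | Seeds above 0.05 |
|---|---|---|---|---|---|
| 0.10 | 5 | 0.141 | 0.980 | 0.012-0.050 | about 2% |
| 0.20 | 5 | 0.200 | 0.962 | 0.0085-0.064 | about 8% |
| 0.36 | 5 | 0.268 | 0.933 | 0.006-0.086 | about 15% |
| 0.20 | 50 | 0.063 | 0.996 | 0.018-0.034 | essentially none |
| 0.20 | 100 | 0.045 | 0.998 | 0.020-0.031 | essentially none |
| 0.36 | 100 | 0.060 | 0.996 | 0.018-0.034 | essentially none |

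Example at FMI 0.20, m = 5: SD = sqrt(0.20/5) = 0.200; 2.241 - 0.392 = 1.849 gives p = 0.064; 2.241 + 0.392 = 2.633 gives p = 0.0085.

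**Simulation check.** One borderline data set was simulated with 330 per arm, eight countries (assumed), one baseline covariate and 20% of outcomes missing at random (mean FMI about 0.2). It was imputed repeatedly.

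- At m = 5 (600 seeds), 95% of p-values lay between 0.019 and 0.169, and 35% of seeds were below 0.05.
- At m = 50 (150 seeds), the range was 0.041 to 0.077, and 25% were below 0.05. The median there was 0.056, so this data set sits almost on the threshold. A larger m narrows the spread but cannot settle such a case.
- In a data set with a clear effect (median p about 0.001), all 600 seeds at m = 5 stayed below 0.05.

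**Logistic model against CMH.** In 1000 complete simulated trials, logistic regression with treatment and country was compared with the CMH test stratified by country. The mean absolute difference in z was 0.008 (maximum 0.017), and the decision at 0.05 agreed in 99.5% of trials.

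**The case against.** The strongest reply is that little depends on this. It is one of three sensitivity analyses, and no success rule attaches to it. The Worst Case primary analysis and its type I error are untouched. The pooling rules already allow for a finite number of imputations through the (1 + 1/m) term and the t reference, so the m = 5 analysis is valid, only imprecise. Every finite m depends on the seed to some degree. At the planned effect the expected z is 3.29, which is (3.29 - 1.96)/0.20 = 6.7 seed SDs from the threshold at FMI 0.20. All of this stands, and it limits the point to borderline results.

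Missing information may also be well below the drop-out share. Subjects who start rescue medication or have surgery are failures by rule, section 4.5 asks for end-of-treatment assessments after withdrawal, and diary data up to withdrawal can inform the imputation. That stands too. At FMI 0.10 only about 2% of seeds cross from p = 0.025.

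Three stronger readings are tempting, and the protocol does not support them.

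- *The logistic model makes this an unlike comparison with the primary.* With treatment and country in the model it agrees almost exactly with the stratified CMH test. Section 8.6 already requires adjustment for country, and section 8.6.1 itself plans logistic regression for the case of confounding: "then logistic regression will be performed using the background variables as covariates". The comparison would drift only if country were left out or if baseline values (section 8.7.1) were added, since the odds ratio would then be conditional on them. The unlisted terms can be settled in the SAP.
- *The analysis should pool a CMH risk difference because that is the primary estimator.* Section 8.6.1 names a CMH test and no risk-difference estimator. MIANALYZE pools estimates with standard errors, so a log odds ratio is an ordinary choice.
- *The plan expects 20% loss by Week 16 and 36% by Week 52.* Section 8.2 gives a single 20% factor for both phases. The 36% comes from 1 - 0.8 x 0.8. It fits the Week 52 number (330 x 0.64 = 211, against 210) but not the Week 16 number (330 x 0.8 = 264, against 240). Here 0.36 is only the upper end of an assumed range.

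**Conclusion.** The point holds as a minor one. Five imputations give a between-seed SD of the pooled z of about 0.14 to 0.27 for FMI 0.10 to 0.36, enough for a borderline sensitivity result to change sides of 0.05 on a rerun. The size rests on the assumed FMI and on the illustrative p-value of 0.025; the formula treats the standard error as fixed.

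A reader might infer that the trial's conclusion depends on a random seed, or that this analysis can neither support nor contradict the primary result. Neither follows. The primary result has no random element, and a clear effect stays clear at m = 5. The analysis is unreliable as a check only when its result is close to 0.05.

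**What to change.** In section 8.7.2, replace 5 imputations with a fixed number of about 50-100, for example 100, and state that the seed is prespecified; its value can be set in the SAP. The larger number reduces the noise. The seed makes the reported figure reproducible even when it falls very near 0.05.

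Keep PROC LOGISTIC. As a clarification, state that the pooled model carries treatment and country, so that it matches the country-stratified CMH test, and that any version with baseline values is reported separately.

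The cost is two lines of text and computing time. No data collection, sample size or primary analysis changes.
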